7.1. Summary

Safety measures will include:

- Adverse events query (Visits 1, 3, 4 and 6)
- Habitual distance visual acuity, BCVA (Visits 1, 3, 4 and 6)
- Intraocular pressure, IOP (Visits 1 and 6)
- Retinal imaging and ocular fundus examination (Visits 1 and 6)
- Basic blood tests (Visits 2 and 5)

7.2. Data Monitoring

This study is a single-site, investigator-initiated clinical trial (with procedures being undertaken at two Melbourne locations – St Vincent's Hospital and the University of Melbourne). [name], Director - Director, Department of Endocrinology and Diabetes at St Vincent's Hospital, will act as the medical safety monitor for the trial. He possesses the requisite expertise to assist and advise the HREC about reports of serious adverse events. All adverse events will be discussed by the Principal Investigator ([name]) and the medical monitor before reporting to the relevant HREC or other regulatory agencies, as required.

7.3. Adverse events (AEs)

7.3.1. Assessments and documentations of adverse events

All AEs and SAEs will be immediately (within 24 hours) reported to the Principal Investigator by the research team member.

At Visit 1, after informed consent and before the initial study products are administered, all pretreatment adverse events will be documented (e.g., allergic response to topical anaesthetic). Conditions that are present at screening and do not deteriorate will not be considered adverse events.

After the study product supply, all treatment-emergent post-treatment adverse events will be documented. Abnormal laboratory values will not be considered adverse events unless deemed clinically significant by the medical monitor, and documented as such.

If adverse events occur, the first concern will always be the safety of the study participants. All adverse events, including severity, action taken and likely relationship to the study product will be documented throughout the study.

At each visit, the co-investigator or principal investigator will begin the examination by querying for adverse events by asking each participant a general, non-directed question such as "How have you been feeling since the last visit?" Directed questioning and examination will then be carried out as appropriate.

The description of each AE recorded will include:

- A description of the AE;
- The onset date, duration, date of resolution;
- Severity (assessed as per section 7.4;
- Seriousness (i.e., is it an SAE?);

nPROOFS1-v1.2 [01-July-2018] Page 23 of 53

- Actions taken;
- The outcome;
- The likelihood of the relationship of the AE to the study treatment (Unrelated, Possible, Probable, Definite).

For each adverse event reported, the number and percent of participants affected will be tabulated. Separate adverse event tables will be generated for pre-treatment AEs and post-treatment AEs. All adverse events will be presented in the listings. Other safety variables, including biomicroscopy findings, BCVA, IOP, retinal fundus photograph and blood test results will be analysed.

DEFINITIONS:

• An adverse event is **any** untoward medical occurrence in a participant or clinical investigation of participant administered a pharmaceutical product. It does not necessarily have a causal relationship with treatment.

An adverse event can therefore be **any** unfavourable or unintended sign, symptom, or disease temporally associated with the use of a study (investigational) product, whether or not it is thought to be related to the study (investigational) product. In addition, during the screening examination (Visit 1), pre-treatment adverse events will be assessed regardless of the administration of a pharmaceutical product.

All adverse events judged as having a reasonable possibility of a causal relationship to an investigational medicinal product will qualify as adverse reactions. The expression 'reasonable causal relationship' means to convey, in general, that there is evidence or argument to suggest a causal relationship.

Note: Details relating to adverse events must be collected once informed consent has been obtained, regardless of whether or not the patient has been administered study product. Progression of treatment indication including new or worsening of anticipated clinical signs or symptoms, which are collected as clinical efficacy variables and assessed as unequivocally associated with the disease progression and /or lack of efficacy, should NOT be reported as adverse events unless the disease progression is greater than anticipated in the natural course of the disease.

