10.2. Informed consent and privacy

After the study is discussed with the potential participant, a person wishing to participate must provide written informed consent prior to any study-related procedure being undertaken. Each potential participant who provides informed consent will be assigned a participant ID code that will be used on all documentation and labelling related to this study. Eligible participants will also be assigned a randomisation number that will be used to assign treatment throughout the study.

After informed consent is obtained at Visit 1 and before randomisation into the study occurs, all pre-treatment adverse events will be documented.

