10.4. Visits and associated procedures

Clinical evaluations are intended to be performed by the same clinician throughout the study, whenever possible. If it is not possible to use the same evaluator to follow the patient, then evaluations should ideally overlap (i.e., examine the patient together and discuss findings) for at least one visit.

Visit 1 (including Screening), The University of Melbourne, 2 hours

The following procedures will be performed at Visit 1

- Written informed consent
- Demographic information
- Medical and ophthalmic histories
- Inclusion/exclusion criteria assessment
- Pre-treatment adverse event assessment
- Diet questioning
- Urine pregnancy test (for females of childbearing potential only)
- Habitual/ best corrected visual acuity
- MNSI questionnaire
- OSDI questionnaire
- EQ-5D-5L questionnaire
- iMTA questionnaire
- Tear osmolarity
- Basal (non-stimulated) tear collection
- Non-contact aesthesiometry

nPROOFS1-v1.2 [01-July-2018] Page 30 of 53

- Slit lamp assessment
- Anterior chamber angle assessment
- TRUT
- Ocular surface staining (Oxford scale)
- IOP (with anaesthesia and fluorescein using a Goldmann tonometer)
- Corneal confocal microscopy (with anaesthesia)
- Dilated fundus examination (with mydriatic eye drops) and non-invasive retinal imaging
- Pin-prick blood sample for omega-3 fatty acid analysis
- Re-check all eligibility requirements
- Dispense masked study products (if the participant meets the required qualifications)

Randomised participants will be provided with a supplement intake log (to mark off when they consume their supplements each day), given instructions with regard to how to take their supplements and be advised about the dose regimen to be followed. The supplement label (which specifies details with regard to: optimal storage conditions, clinical trial use only, keep out of reach of children, etc.) should also be read through and explained with the participant.

Participants will be asked to commence taking oral supplements (Day 1) on the day that their baseline nerve functions tests are conducted at Visit 2.

Visit 2 (Day 1; St Vincent's Hospital, 2 hours)

This visit will assess peripheral nerve fibre function, as per routine nerve conduction examinations, for diabetic neuropathy. The following procedures will be performed at this visit:

- Brief medical history (including related neuropathy symptoms)
- Michigan Diabetic Neuropathy Score
- Cutaneous silent period testing

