10.5. Instructions to eligible participants

Eligible participants will be asked to attend a total of 6 study visits; four visits will be at the University of Melbourne, and two will be performed at St Vincent's Hospital (at the start and end of the supplementation period), within four weeks of the initial and final visits.

At Visit 1, eligible participants will be dispensed study products consisting of their randomised treatment allocation. Study investigators will counsel the participant to consume 2 capsules each day, with or without food, at least two hours before or after medications. Participants will be provided with a supplement log to document their consumption of capsules each day. Participants will be advised not to 'make up' for missed doses with additional capsules on a given day; a reason for a 'missed dose' should be documented on the supplement log, which will be returned along with any remaining capsules at Visits 3, 4 and 6.

An appointment will be arranged for participants within four weeks of Visit 1, to attend Visit 2 at St Vincent's Hospital, Melbourne. Participants will be asked to start their first dose on the day of Visit 2 (Day 1), following their assessments at St Vincent's Hospital. Participants will be advised that they should maintain their regular dietary habits and medications (including ocular and systemic) and notify us of any change in medications of dosage throughout the study.

Appointments for Visits 2 and 5 at St Vincent's Hospital will be arranged for the participants by the study investigators, at Visits 1 and 4 respectively.

Participants will be encouraged to contact the Principal Investigator at any time should they have any questions about the study or the instructions they have been given.

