The compliance outcomes (such as the percentage of omega-3 and omega-6 fatty acids present in erythrocytes (determined from dried blood spot tests [analysed by Waite Lipid Analysis Services, Australia]) at the study endpoint (day 180) will be analysed using a linear regression model, adjusted for baseline. Before fitting this model, the distribution of the outcome will be explored. In addition, we will examine if there are potential violations of underlying model assumptions (e.g., residuals). As a result, we may apply an appropriate transformation (e.g., log-transformation) before fitting the final model. The proportion of returned capsules (counted by an independent, masked reconciler) will be summarised by treatment group.

Compliance (%) will be derived as 100 times [(actual number of capsules taken over the study period) divided by (total number of capsules that should have been taken over the study period)], with study period based on actual trial participation duration. The actual number of capsules taken over the study period is derived as the number of capsules dispensed minus the number of capsules returned. Participants with compliance less than 75% or above 125% will be considered as non-compliant to study drug intake (AusPAR2011; NCT01797185). A sensitivity analysis will be performed for the primary outcome to examine the treatment effect when non-compliant cases are excluded from the analysis.

Concomitant medications

Concomitant medications will be categorised by their therapeutic class, according to the United States Pharmacopeia Drug Classification system. The number and percentage of participants taking concomitant medications in each class, for each participant group, will be tabulated and reported in the supplementary information.

Adverse events

Information about adverse events will be collated, summarised and provided in the supplementary information. The incidence of participants with adverse events at each visit, type of event, event severity, and a judgement regarding its association with the investigational product or a study procedure, will be tabulated and reported in the supplementary information.

7. Measures to Adjust for Multiplicity, Confounders, Heterogeneity

Adjustments for confounders

In addition to the models specified above that only include treatment group, we will fit two adjusted models to the outcomes linked to the primary, key secondary, and secondary aims that adjusts for:

Adjusted model 1:

- Age (years)

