Tolerance windows will be used for converting visit dates into visit numbers according to the study visit schedule before summarising or analysing the data. The relative day of testing will be derived as the visit date minus the supplementation start date. The visit windows in Table 1 will be applied to the testing dates.

Table 1. Visit windows

Visit	Target day	Lower limit (incl.)	Upper limit (incl.)
Day 1	Supplement start date (Day 0)	Day -35	1
Day 30	Day 30	Day 14	Day 44
Day 90	Day 90	Day 76	Day 104
Day 180	Day 180	Day 156	Day 204

Assessments performed outside of these visit windows will not be included in the analyses. If a participant has more than one assessment performed within the same visit window, then the assessment closest to the target date will be used. The visit windows will be applied to the study variables described in Appendix 1.

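### The treatment-emergent adverse event period starts at product supply (Visit 1), not first dose (Visit 2), and the SAP sets no onset rule, so pre-dose events can enter the comparison between arms

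*Combined protocol and SAP*

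**What the plan says.** **Cut-point.** Protocol 7.3.1 handles the two periods in consecutive paragraphs. For the first: "At Visit 1, after informed consent and before the initial study products are administered, all pretreatment adverse events will be documented". For the second: "After the study product supply, all treatment-emergent post-treatment adverse events will be documented". Section 10.2 describes the first period differently, with recording after consent and "before randomisation into the study occurs, all pre-treatment adverse events will be documented".

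**Supply and first dose.** Section 10.5 says: "At Visit 1, eligible participants will be dispensed study products consisting of their randomised treatment allocation". Dosing waits for the next visit, by section 10.4: "Participants will be asked to commence taking oral supplements (Day 1) on the day that their baseline nerve functions tests are conducted at Visit 2". Section 10.5 places that visit within four weeks of Visit 1. The visit schedule (protocol 4) labels Visit 1 as Day -35, and the baseline window in SAP section 10, Table 1 also opens at Day -35, counted from the supplement start date.

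**Timing of the outcome.** Protocol 5.2 lists reported adverse events as a safety outcome, measured as change from Day 1 at Days 30, 90 and 180.

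**Collection.** Section 7.1 lists the adverse event query at Visits 1, 3, 4 and 6. Sections 10.4 and 11.1.2 agree with that list. Section 7.3.1, however, has the investigator open every visit with the query.

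**Analysis.** Section 7.3.1 promises separate tables for pre-treatment and post-treatment events. SAP 6.5 plans to tabulate "The incidence of participants with adverse events at each visit, type of event, event severity, and a judgement regarding its association" with product or procedure. It has no onset condition and does not define treatment-emergent. SAP Appendix 4 has a dedicated adverse event table (S2) and adverse event rows in Table 5, neither split at first dose. The Safety sample in SAP section 3 is as-treated and does not state that a dose must have been taken.

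**The concern.** SAP Aim 3 assesses safety partly through the incidence of adverse events, and the results compare that incidence between arms with p-values. An event that begins before the first capsule cannot be caused by either product. If the period labelled treatment-emergent opens at supply, such events are counted with those on product. The label is then wrong, and a real difference between arms is harder to see on a ratio scale. With 21 and 22 participants, one or two misplaced participants visibly change the percentages. The reader cannot tell whether this happened, because no onset dates or pre/post split are reported.

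**Working it through.** **Inputs.** Longest gap between supply and first dose: 28 days (protocol 10.5) or 35 days (protocol 4; SAP Table 1). Dosing period: 180 days (protocol 3.1), with a final-visit window of Days 156 to 204. Reported participants with at least one AE or SAE: 9/21 omega-3 and 7/22 placebo, p = 0.54 (supplementary Table S3).

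**1. Reproducing the reported figures.** Two-sided Fisher exact tests give:
- any AE or SAE, 9/21 v 7/22: p = 0.537 (reported 0.54)
- any AE, 9/21 v 6/22: p = 0.347 (reported 0.35)
- any SAE, 0/21 v 1/22: p = 1.0 (reported 1.0)

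**2. Undosed share of the counted time.** Share = gap / (gap + dosing days).
- 28 / (28 + 180) = 28/208 = 13.5%
- 35 / (35 + 180) = 35/215 = 16.3%
- Final visit at Day 156 or 204: 15.2% to 12.1% for a 28-day gap, 18.3% to 14.6% for a 35-day gap
- Gap of 0: 0%

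These are ceilings, because they put every participant at the longest gap.

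**3. First follow-up interval.** If adverse events are not queried at Visit 2, and Visit 3 falls on its target day, at most 35 / (35 + 30) = 53.8% of the recall period at Visit 3 is undosed. If Visit 2 includes the query, this figure does not apply.

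**4. Expected number of participants.** Assume a constant event rate and the longest gap for everyone. Of the 16 participants with an event (9 + 7), about 16 × 28/208 = 2.2 to 16 × 35/215 = 2.6 would have had it in the gap.

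**5. Dilution.** Assume a 35-day gap, equal background rates, and a true rate ratio of 2.0 after dosing. The rate ratio over the whole counted period is (35 + 2 × 180) / (35 + 180) = 395/215 = 1.84. For a 28-day gap it is 388/208 = 1.87. With the placebo rate set so that 7/22 have an event over 215 days, the ratio of proportions falls from 1.73 to 1.59, but the difference in proportions only from 0.199 to 0.187.

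**6. Sensitivity of the reported comparison.** Suppose 0 to 3 participants per arm had only pre-dose events. Fisher p then ranges from 0.10 (9/21 v 4/22) to 1.0. Two illustrations:
- two removed from omega-3 only: 7/21 (33%) v 7/22 (32%), p = 1.0
- two removed from placebo only: 9/21 (43%) v 5/22 (23%), p = 0.20

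The percentages move noticeably, but no result crosses 5%. The actual corrected counts cannot be computed, because onset dates are not given.

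**The case against.** The best defence is that the protocol can be read the other way. The sentence on product supply says when treatment-emergent events will be documented, and does not strictly say that every later event is one. The preceding paragraph of 7.3.1 ends the pre-treatment period when product is administered. Section 10.2 says when early events are recorded, not when that period closes. Section 5.2 counts from Day 1. This shows that the passages conflict, but it does not supply a rule. The administered wording is tied to Visit 1, where product is only dispensed. Day 1 is also used loosely for baseline, which includes Visit 1 measurements. No passage states an onset rule based on first dose.

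A reader might infer four stronger points that the documents do not support.
- *That gap events are first asked about at Visit 3.* The visit lists suggest this, but 7.3.1 calls for a query at every visit, and Visit 2 includes a brief medical history. The documents conflict.
- *That pre-dose events cannot be judged for relationship to product.* Onset date and relationship are recorded for each event, and the SAP visit windows require the supplement start date. An event before the first capsule can simply be judged unrelated to product. Table S3 separates unrelated from potentially related events; the latter are only nausea, 2 v 1.
- *That the reported table contains pre-dose events.* Its summary of all events sits above the unrelated and potentially related subsections, so all may mean no more than both kinds together.
- *That the comparison is biased for one arm.* Allocation is randomised and masked, so gap events are expected equally in both. A ratio is diluted, while the expected difference in event rates over the dosed period is carried through unchanged.

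Collecting adverse events from consent onward is proper. The fault lies in how they are labelled and analysed.

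**Conclusion.** The point stands as a fault of definition. The protocol's stated cut-point is supply, supply precedes the first dose by up to 28 or 35 days, and the SAP neither corrects this nor carries over the split that the protocol promised. Followed as written, the plan lets events in undosed participants count in the Aim 3 comparison.

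The effect is modest: at most 13.5% to 16.3% of the counted time at the longest gap with 180 days on product, and possibly none. The number of events affected is unknown and could be zero. The dilution estimate rests on a constant background rate, everyone at the longest gap, and an assumed rate ratio of 2.0. Moving up to three participants per arm changed no 5% conclusion. The correction is worth making because a safety table in a trial this small is read for its counts and percentages more than for its p-values.

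**What to change.** 1. In protocol 7.3.1 and SAP 6.5, define treatment-emergent as onset or worsening on or after the supplement start date. Align 10.2 and 5.2 with that definition.
2. Base the between-arm adverse event table on those events. List events from consent to first dose in the separate pre-treatment table that 7.3.1 already promises.
3. Reconcile the every-visit query in 7.3.1 with sections 7.1, 10.4 and 11.1.2, and state whether adverse events were queried at Visit 2. Reconcile the four-week gap in 10.5 with Day -35 in the schedule and SAP.

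**Cost.** A few sentences, one re-run table and one short listing. Onset and start dates are already collected. A date of worsening is not among the fields listed in 7.3.1, so those cases may need the source records. Reported event counts may fall slightly. The last participant's last visit was on 10 March 2020, so adding a Visit 2 question could help only a future study.

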7.3.2. Serious adverse events (SAEs)

- A serious adverse event is any adverse event that results in any of the following outcomes:
 - o death
 - o a life-threatening adverse event
 - o inpatient hospitalisation or prolongation of existing hospitalisation (for any reason)
 - o a persistent or significant disability/incapacity
 - o a congenital anomaly/birth defect
 - a diagnosis of cancer
 - o any abortion (spontaneous or non-spontaneous)

• A Suspected Unexpected Serious Adverse Reaction (SUSAR) is any SAE that is both suspected to be related to the study treatment and is unexpected (i.e., not consistent with applicable product information)

Important medical events that may not result in death, be life-threatening, or require hospitalisation may be considered a serious adverse event when, based upon appropriate medical judgment, they may jeopardise the participant or may require medical or surgical intervention to prevent one of the outcomes listed in this definition. (See below for procedures for reporting a serious adverse event.)

Pre-planned surgeries or procedures for pre-existing, known medical conditions, for which a participant requires hospitalisation are not reportable as a serious adverse event. Any pre-planned surgery or procedure should be clearly documented in the site source documents by the medically qualified investigator at the time of the participant's entry into the study. If it has not been documented at the time of the patient's entry into the study, then it should be documented as a serious adverse event and reported as such.

7.4. Severity of AEs

A clinical determination will be made of the intensity of **every** adverse event. The severity assessment for a clinical adverse event must be completed using the following definitions as guidelines:

- Mild awareness of sign or symptom, but easily tolerated.
- Moderate discomfort enough to cause interference with usual activity.
- Severe incapacitating with inability to work or do usual activity.
- Not applicable in some cases, an adverse event may be an 'all or nothing' finding which cannot be graded.

